Official Title of the Study: Transmitted Light Tissue Analysis (TiLTT) (TiLLT)

Document Date: January 15, 2015

NCT Number: NCT02749201

Transmitted Light Tissue Thickness Analysis (TiL/TT) (TiLLT)

The most common surgical procedure for weight loss is the sleeve gastrectomy. The laparoscopic sleeve gastrectomy (LSG) involves the linear stapling of the stomach using a stapling device [e.g. Echelon (Ethicon Somerset NJ)] fired multiple times along the length of the stomach thereby excising 80-90% of the stomach leaving the patient with a "sleeve" of stomach rather than the normal anatomical pouch. The gastric wall varies in thickness and thus there are a varied staple sizes available for this use. Staple sizes range from 2.0mm-5.0mm in height. In standard surgical practice the surgeon chooses the size of staple cartridge for each subsequent firing based on his experience and estimations about the thickness of the stomach tissue in any given region. The drawback of this technique is that it is highly inaccurate. If the surgeon's estimation is in error, the staple height chosen may be either too tall or too short leading to bleeding or leakage from between the staples or malformed/unformed staples leading to staple line failure. Any of these errors can lead to devastating complications such as hemorrhage, leak, sepsis and death. To date there is no objective way to measure the thickness of the tissue being stapled and thus staple choice relies entirely on surgeon estimation which is inherently inaccurate. We hypothesize that a light source placed in the stomach lumen will transmit light through the gastric wall. The amount of light transmitted, i.e. visible to an imaging device arrayed external to the stomach, will be directly proportionate to the thickness of the stomach. This study will take advantage of the fact that during routine procedures in the sleeve gastrectomy procedure a lighted tube is placed into the gastric lumen via the mouth. This device is called the Gastrisail and has 10 separate LED lights arrayed along its length. This allows for the measurement of transmitted light intensity through the gastric wall at 10 individual locations along the length of the stomach. In addition this study will take advantage of the fact that during standard practice in a sleeve gastrectomy a section of the stomach corresponding to the location of the lights is excised and sent for pathological evaluation. This will allow us to measure the actual thickness of the stomach at 10 points corresponding to the locations of the transmitted light intensity. For this measurement we will use a standardized and validated measurement tool/calipers. Now with two sets of numbers we plan to correlate the degree of transmitted light intensity with actual thickness measurements and thereby reach an algorithm which will allow the transmitted light intensity data alone to predict gastric wall thickness. This will provide the surgeon with an entirely non-invasive objective measure of gastric wall thickness and hopefully improve his/her choice of staple size during these surgical procedures thus improving safety.

The aim of this project is to create a noninvasive method of predicting the thickness of the gastric wall. This information can then be used to aid the surgeon in picking the correct size staple cartridge when stapling the stomach during sleeve gastrectomy surgeries.

Methods: We propose to use a standard gastric sizing bougie (plastic guide placed into the stomach at the time of stapling designed to help outline a standardized staple line) used in

common surgical practice (Gastrisail, Covidien). This bougie comes with 10 LED lights arrayed along its length. The wavelength and light intensity of these LED's is standardized. The bougie is routinely placed via the mouth, down the esophagus and into the distal stomach. the bougie will be retained in place throughout the stapling process as per standard technique. The use of the bougie is part of the standard procedure of sleeve gastrectomy and is used in 100% of all sleeve operations.

Using a standard high definition laparoscope, images of these lights within the gastric lumen will be captured. The images will then be uploaded and processed using a software package provided by ImageIQ, Inc. The software will measure the light intensity at each of the 10 LED positions on the bougie, thereby obtaining 10 individual intensity readings at 10 different sites along the length of the stomach.

There will be no measurements made on the in-vivo stomach but simply an image made of the stomach with the lighted bougie in-situ. The analysis of the light intensity from the image and data extraction will be done after the completion of the surgery using software provided by the ImageIQ corporation.

The stomach will be stapled as per standard surgical routine and the specimen side of the gastric body will be separated from the remnant stomach and removed from the abdominal cavity as per standard surgical practice. Prior to this specimen being sent to the pathology department, on the back table, a standardized, validated thickness measuring tool will be used to measure the thickness of the gastric specimen ex-vivo at the identical 10 points as light intensity imaged at the LED's.

A mathematical formula will then be created to correlate the data obtained by light transmittance through the gastric wall and the mechanical measurements of the gastric specimen we obtained using a scientific calipers. The formula will be derived as a directly proportional calculation with where $y=kx$ and k is a non-zero constant.

This predictive algorithm will allow non-invasive gastric wall thickness measurements in real-time based solely on imaged light transmittance using nothing more than a standard lighted bougie and standard laparoscope.

The study will be conducted in the operating room and will have two halves of data collection. Firstly there will be images taken intraoperatively of the lighted bougie while in proper position within the gastric lumen. Secondly there will be gastric wall thickness measurements taken of the explanted stomach specimen on a back table in the operating room prior to it being sent to the pathology department. This data collection will yield 20 measurements per patient (10 from each of these two sources). Thus each patient will be enrolled in the study only intraoperatively. Following collection of the data for all included patients (see below statistical methodology) the data from each of these sources will be analyzed and the predictive algorithm constructed.

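### A single correlation over all light-thickness pairs would mix patient differences with regional differences, so it cannot by itself support a site-by-site claim

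*Combined protocol and SAP*

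**What the plan says.** The document is short and its sections are unnumbered.

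- **Intended use (opening background section).** At present "the surgeon chooses the size of staple cartridge for each subsequent firing", relying on "estimations about the thickness of the stomach tissue in any given region". The light method is meant to inform that choice.
- **Data (Methods, and the closing paragraph on study conduct).** The software reads each LED position, "thereby obtaining 10 individual intensity readings at 10 different sites along the length of the stomach". Thickness is measured at the same 10 points on the specimen. "This data collection will yield 20 measurements per patient (10 from each of these two sources"), which makes 10 pairs per patient, all from one stomach.
- **Analysis (background and Methods).** "we plan to correlate the degree of transmitted light intensity with actual thickness measurements". Then: "The formula will be derived as a directly proportional calculation with where $y=kx$ and k is a non-zero constant".
- **Reference to further detail (study conduct).** "Following collection of the data for all included patients (see below statistical methodology"). No such section follows in the supplied text.

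The supplied text names no patient effect, repeated-measures method or within/between split. It does not say in so many words that all pairs are pooled.

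**The concern.** The 10 pairs from one patient are not 10 separate pieces of evidence on one question. Across all pairs, light and thickness can be associated for two reasons. Patients with thicker walls may give different light readings from patients with thinner walls. Within one stomach, thicker regions may give different readings from thinner ones. The two associations can differ in size and even in sign.

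An absolute thickness at a given site is the patient's average plus the regional deviation, so both associations are relevant to prediction. Only the second shows whether light distinguishes one firing site from the next. If a single coefficient is reported, a reader cannot tell which of the two produced it. The study could then claim prediction by site when it has shown only that light separates thicker-walled from thinner-walled patients.

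**Working it through.** **Stated figure.** 10 light + 10 thickness = 20 measurements per patient, as the plan says. The plan gives no number of patients, standard deviations (SDs), intraclass correlation (ICC) or target correlation. Everything below therefore rests on assumed values and shows what is possible, not what this study will find.

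**Identity.** With pairs nested in patients, the large-sample pooled correlation is

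r_pooled = ρ_between × √(ICC_light × ICC_thickness) + ρ_within × √((1 − ICC_light)(1 − ICC_thickness)).

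A sizeable r_pooled is compatible with ρ_within = 0.

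**Illustration 1: light tracks only the patient mean.** Assumed: 20 patients × 10 sites; thickness = 2.5 mm + patient effect (SD s_b) + site effect (SD s_w); light = patient effect + noise SD 0.1. Light is scored so that higher means thicker; the sign does not affect the argument. The limit is

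r_pooled = s_b² / √[(s_b² + s_w²)(s_b² + 0.1²)].

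For 0.5/0.5: 0.25 / √(0.50 × 0.26) = 0.25 / 0.3606 = 0.69.

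| s_b / s_w (mm) | Limit of pooled r | Mean pooled r, 400 simulated trials | Within-patient r |
|---|---|---|---|
| 0.3 / 0.6 | 0.42 | 0.41 | 0.00 to 0.01 |
| 0.5 / 0.5 | 0.69 | 0.67 | 0.00 |
| 0.6 / 0.3 | 0.88 | 0.87 | 0.00 |

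The true within-patient correlation is zero in every row.

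In the 0.5/0.5 case, a straight line fitted with an intercept also lowers the prediction error in left-out patients, from 0.71 to 0.51 mm. That gain in absolute prediction is real, but none of it is regional information.

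**Illustration 2: less extreme between-patient correlation.** With ρ_within = 0 and the same ICC for light and thickness, the identity reduces to ρ_between × ICC:

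| ρ_between | ICC 0.3 | ICC 0.5 | ICC 0.7 | ICC 0.8 |
|---|---|---|---|---|
| 0.5 | 0.15 | 0.25 | 0.35 | 0.40 |
| 0.7 | 0.21 | 0.35 | 0.49 | 0.56 |
| 0.9 | 0.27 | 0.45 | 0.63 | 0.72 |

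The distortion shrinks as the ICC falls, that is, as patients become more alike in mean light and mean thickness.

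**Illustration 3: the opposite direction.** Light follows thickness at every site (SDs 0.5/0.5 mm, light noise 0.2) but carries a patient-level brightness offset. Within-patient r is √(0.25/0.29) = 0.93 throughout. The pooled limit is √[0.50 / (0.54 + offset SD²)]:

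- offset 0: √(0.50/0.54) = 0.96
- offset 0.5 mm: √(0.50/0.79) = 0.80
- offset 1.0 mm: √(0.50/1.54) = 0.57

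At 1.0 mm, simulated error in a left-out patient is about 0.60 mm from the pooled line. It is still about 0.52 mm when patient-mean light and deviation from that mean have separate slopes. Without any offset it is about 0.19 mm under either approach. The offset lowers the correlation and also genuinely worsens absolute prediction.

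**The case against.** **Pooling is inferred.** The plan never says that all pairs enter one correlation, and the section it refers to might specify something else. This stands as a caveat. The single k is explicit, however, and no patient-level term appears in the supplied text, so one analysis over all pairs is the natural reading.

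**Between-patient information is part of the target.** Staple sizes are absolute heights (2.0 to 5.0 mm in the background section), and the aim is to predict wall thickness. Knowing only which region is relatively thicker does not give a height. This stands: a reader might infer that the question is purely within-patient and that patient differences are mere contamination, and the documents do not support that. What remains is that the two sources should be visible separately, because the intended choice is made firing by firing.

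**The illustration is extreme.** Light that follows the patient mean almost perfectly and ignores the local wall is a bounding case. Each LED is read at its own site and the light source is standardized. The prediction errors above come from lines with an intercept, not from the planned proportional formula. Both points stand. The identity does not depend on that case, and the milder settings show the same effect at smaller size.

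**Brightness offsets.** A reader might infer from the third illustration that a usable method would be discarded. The documents do not support that. The plan wants thickness from imaged light alone and describes no calibration per patient, so a low pooled r there largely reflects poor absolute prediction in a new patient.

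**Conclusion.** The concern holds in limited form. As supplied, the plan could yield a correlation that looks strong without showing that light distinguishes regions of one stomach, and that is what a site-by-site claim needs. Under the assumed extreme case, pooled r is about 0.41 to 0.87 with no within-patient association. Under the milder assumptions it is 0.15 to 0.72.

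The size in this study cannot be computed, because the documents give no variance components and no number of patients. It would be small if patients differ little in mean light and mean thickness. A reader might go further and conclude that the study's correlation will be spurious, and nothing in the documents shows that. The point is a worthwhile, low-cost improvement to the analysis and to the wording of the conclusion. If the missing methodology section already separates the two levels, the sponsor need only confirm it.

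**What to change.** Keep the planned prediction formula and report the following beside it, from the same data:

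1. **Within-patient association:** a repeated-measures correlation, or the slope on each LED's light minus that patient's mean light, from a model with a random patient intercept.
2. **Between-patient association:** the slope on patient-mean light.
3. **Confidence intervals** for both that account for clustering by patient.

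State in advance that site-by-site prediction will be claimed only if the within-patient association supports it, and that otherwise the conclusion is limited to average wall thickness per patient. Supply the statistical methodology section to which the study-conduct paragraph refers, or confirm what it says on this point.

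Cost: a little more analysis, with no new patients, measurements or procedures. The headline correlation may turn out less favourable than the pooled one.

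### One light value per LED site leaves the new method's frame-to-frame repeatability unestimable, and frame noise lowers the observed correlation

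*Combined protocol and SAP*

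**What the plan says.** The combined protocol and SAP has unnumbered sections. In the Methods section, on image capture:

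- On how light is recorded: "images of these lights within the gastric lumen will be captured". A later paragraph describes the same step in the singular: "There will be no measurements made on the in-vivo stomach but simply an image made of the stomach with the lighted bougie in-situ".
- On what the software delivers: "thereby obtaining 10 individual intensity readings at 10 different sites along the length of the stomach".
- On the light source: "The wavelength and light intensity of these LED's is standardized".
- On the analysis: "The formula will be derived as a directly proportional calculation with where $y=kx$ and k is a non-zero constant". The text does not say which of light and thickness is x and which is y.

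The closing paragraph on data collection gives the total: "This data collection will yield 20 measurements per patient (10 from each of these two sources". The opening section states the goal, which is to "reach an algorithm which will allow the transmitted light intensity data alone to predict gastric wall thickness".

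The supplied text contains no repeat image, averaging rule, repeatability check or measurement-error term. The closing paragraph points to a statistical methodology that is not in that text.

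**The concern.** Light intensity is the new method under test. A reading may reflect the capture conditions of its frame (camera distance, angle, exposure) as well as the wall. Standardised LEDs control variation at the source, but nothing in the plan controls or measures variation at the camera.

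With one light value per site, a poor fit has three possible sources: frame noise, caliper error, or a true failure of light to track thickness. The planned data cannot separate frame noise from the other two, and only frame noise can be reduced by averaging frames. Nor can the trial say whether a second image of the same stomach would give the same predicted thickness. That matters for a tool meant to guide staple choice during the operation. Because intensities are extracted after surgery, the information is lost for good if only one frame per site was stored.

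**Working it through.** **1. The plan's own count.** 10 sites × 1 light value + 10 sites × 1 caliper value = 20, which matches the stated total. With m light values per site, the total is 10m + 10, and each patient contributes 10(m − 1) degrees of freedom to the within-site light variance:

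- m = 1: 20 values, 0 degrees of freedom
- m = 2: 30 values, 10 degrees of freedom
- m = 3: 40 values, 20 degrees of freedom

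**2. Effect on the correlation.** Let R be the reliability of one frame, that is, the share of the variance in readings that is not frame noise. The documents give no R, so a range is assumed. A true correlation of 0.80 is also assumed.

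- Reliability of the mean of m frames (Spearman-Brown, independent errors): R_m = mR / (1 + (m − 1)R)
- Observed correlation = true correlation × √R_m

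Example with R = 0.7 and m = 3: R_m = 2.1 / 2.4 = 0.875; √0.875 = 0.935; 0.80 × 0.935 = 0.748.

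| R (assumed) | Multiplier, 1 frame | Observed r, 1 frame | R_m, 3 frames | Multiplier, 3 frames | Observed r, 3 frames |
|---|---|---|---|---|---|
| 0.5 | 0.707 | 0.566 | 0.750 | 0.866 | 0.693 |
| 0.7 | 0.837 | 0.669 | 0.875 | 0.935 | 0.748 |
| 0.9 | 0.949 | 0.759 | 0.964 | 0.982 | 0.786 |
| 0.95 | 0.975 | 0.780 | 0.983 | 0.991 | 0.793 |

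**3. Effect on k.** The plan names no fitting method, so least squares through the origin is assumed.

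- *Light as y.* Zero-mean noise unrelated to thickness leaves k unbiased and only less precise.
- *Light as x.* Write CV for the SD of true light divided by its mean, and scale the mean to 1. The noise variance is then s² = CV²(1 − R)/R, and k is multiplied by (1 + CV²) / (1 + CV² + s²/m). Example with CV = 0.3 and R = 0.7: s² = 0.09 × 0.3 / 0.7 = 0.0386. The factor is 1.09 / 1.1286 = 0.966 for one frame and 1.09 / 1.1029 = 0.988 for three.
- *Range with light as x.* For assumed CV of 0.2 to 0.5 and R of 0.5 to 0.9, the factor runs from 0.83 (CV 0.5, R 0.5) to 0.996 (CV 0.2, R 0.9) with one frame. With three it runs from 0.94 to 0.999.

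A simulation at CV 0.3 and R 0.7 agreed. With one frame the correlation multiplier was 0.836, and k was multiplied by 0.966 with light as x and 1.000 with light as y.

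**The case against.** Five counter-arguments deserve an answer.

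- **The plan may store several images.** A reader might infer from the singular wording that only one frame is taken. The documents do not support that: they fix 10 light values per patient and leave the number of images open. The plural may also mean images across patients or along the bougie, so it does not establish repeats either. The point rests on the count of values.
- **The formula may be sound.** A reader might infer that single readings spoil k. The documents do not support that either. If light is y, k is unbiased; if light is x, the shrinkage is modest. A formula fitted to single frames also suits later use with a single, equally noisy frame.
- **Total prediction error can still be estimated.** This is true, since the residuals from single-frame data already include frame noise. What is lost is the ability to attribute that error to a source.
- **The loss may be small.** At R = 0.9 the correlation rises only from 0.76 to 0.79. The documents cannot show which end of the range applies, and repeats are how the sponsor would find out.
- **Averaging may deliver less than the table shows.** Frames from one session share camera settings, operator and bougie position. Errors they share do not average out, so the three-frame figures are upper bounds.

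**Conclusion.** The point stands as a gap in the design that is cheap to close. It does not invalidate the study. The plan provides one light value per LED site and therefore no degrees of freedom for the repeatability of the method it proposes.

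Under assumed reliability of 0.5 to 0.9 and an assumed true correlation of 0.80, frame noise alone would lower the observed correlation to between 0.57 and 0.76. Three-frame averaging would recover at most 0.69 to 0.79. These figures rest on random frame error that is unrelated to thickness and, for the three-frame values, independent between frames. They show a plausible range and are not estimates for this device.

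The point would fall if the statistical methodology that the closing paragraph refers to already provides for repeat readings.

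**What to change.** 1. Before stapling, capture three image sets per patient, moving the laparoscope away and re-aiming it between sets while the bougie stays in place. Re-reading one stored image would show software noise only. If one view does not show all 10 LEDs, do this in a prespecified subset of patients instead.
2. Have the software read all 10 LEDs in each set.
3. Report the within-site repeatability SD and the intraclass correlation, and convert that SD to mm through the fitted formula. The mm figure is |k| × SD if light is x, and SD / |k| if light is y. State that same-session repeats miss errors shared between frames.
4. Say which variable is x and which is y.
5. Fit and report the formula for a single frame, which matches the real-time use described, and for the three-frame mean. State which input each version applies to.
6. If all patients are included, change the closing paragraph to 30 light plus 10 caliper values, 40 in total.

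The cost is a few more stills while the laparoscope and lit bougie are already in place, three times the software reads, and slightly more analysis. More re-aiming is needed if one view does not cover all the LEDs, which is the reason for the subset option.

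### The prediction formula y = kx through the origin makes predicted thickness rise with light; if thicker walls pass less light, it ranks sites backwards and does worse than the mean

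*Combined protocol and SAP*

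**What the plan says.** The opening background paragraph defines the light quantity as what reaches the camera: "The amount of light transmitted, i.e. visible to an imaging device arrayed external to the stomach". It hypothesises that this amount "will be directly proportionate to the thickness of the stomach". The stated aim is an algorithm that will "allow the transmitted light intensity data alone to predict gastric wall thickness", so light is the predictor and thickness the target.

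The Methods section then gives the model: "The formula will be derived as a directly proportional calculation with where $y=kx$ and k is a non-zero constant". It does not say which variable is x and which is y, names no fitting method, and mentions no intercept, inverse or log form.

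The paragraphs after Methods state the intended use: "This predictive algorithm will allow non-invasive gastric wall thickness measurements in real-time based solely on imaged light transmittance". They also point to a statistical methodology further on, but the supplied text ends without one, so nothing there modifies the formula.

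**The concern.** A line through the origin with one coefficient, fitted to two positive quantities, can only slope upwards. It cannot represent a wall that dims the light as it thickens, and it cannot reveal that its own direction is wrong, because k is positive whatever the data show.

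The formula is the study's only output. If light does fall with thickness, a good optical signal would produce a predictor worse than none. The study could then wrongly conclude that the method fails, or issue an algorithm that swaps thin and thick sites.

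Enrolled patients are not exposed to this. Stapling follows standard routine, and of the image analysis the Methods section says that "data extraction will be done after the completion of the surgery". The exposure comes with the later real-time use that the document intends.

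**Working it through.** The plan gives no value of k, no sample size and no attenuation data, so there is no figure of its own to reproduce. The check is algebra, followed by illustrations on assumed values. Write t for thickness and I for imaged intensity.

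**Without any outside premise**

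1. At I = 0 the formula gives t = k × 0 = 0 mm for every k. A wall that blocks all the light is read as having no thickness.
2. Least squares through the origin gives k = Σ(tI)/Σ(I²). Every term is positive, so k > 0. A ratio of means is positive too. The plan requires only that "k is a non-zero constant", but a negative k would predict negative thickness at every site.
3. If x is thickness instead, the fit is I = k₂t with k₂ = Σ(tI)/Σ(t²) > 0, and the prediction I/k₂ also rises with light.

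**With one premise: light falls as thickness rises, so Cov(t, I) < 0**

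4. For any prediction kI,

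 MSE = Var(t) − 2k·Cov(t, I) + k²·Var(I) + (mean residual)².

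 With k > 0 and Cov(t, I) < 0, the second and third terms are positive and the fourth is not negative. MSE therefore exceeds Var(t), the error of predicting the mean. No particular law of decline is needed, and the swapped form is covered by putting 1/k₂ for k.

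**Small worked example (assumed)**

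5. Ten sites are equally spaced from 2 to 5 mm. This is the document's staple-height range, borrowed as a stand-in for tissue thickness. Light is I = 100·exp(−0.5t), without noise.
 - Σ(tI) = 595.12 and Σ(I²) = 4603.94, so k = 595.12/4603.94 = 0.1293.
 - At 2 mm, I = 36.79 and the prediction is 0.1293 × 36.79 = 4.76 mm.
 - At 5 mm, I = 8.21 and the prediction is 0.1293 × 8.21 = 1.06 mm.
 - The terms of the MSE are 0.917 + 2.202 + 1.380 + 0.975 = 5.474, so RMSE = √5.474 = 2.34 mm. Predicting the mean gives √0.917 = 0.96 mm.
 - The rank correlation of predicted with true thickness is −1.
 - In the swapped form, the 2 mm site is read as 8.14 mm and the 5 mm site as 1.82 mm.

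**Larger simulation (assumed)**

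6. Each setting has one million points, with t uniform on 2–5 mm or 1–4 mm, I = exp(−μt + e), μ from 0.2 to 1.0 per mm, and e normal with SD 0.15. All models are fitted to the same data. The mean-only RMSE is 3/√12 = 0.87 mm. RMSE in mm:

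| Model | 2–5 mm | 1–4 mm |
|---|---|---|
| y = kx (x = light) | 1.53–2.87 | 1.32–2.24 |
| Swapped form, inverted | 1.69–4.74 | 1.53–4.18 |
| Mean only | 0.87 | 0.87 |

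Over both ranges, a line with free slope and intercept gives 0.33–0.58 mm and a log-intensity model 0.15–0.57 mm. At μ = 0.5 on 2–5 mm, 2 mm tissue is predicted as 5.0 mm and 5 mm tissue as 1.1 mm.

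7. Five other declining laws were tried with the same noise: linear falls to 80%, 50% and 10% of the light, 1/t, and 1/t². Here y = kx gives 1.20–2.45 mm (2–5 mm) and 1.09–2.26 mm (1–4 mm). The free line gives 0.29–0.80 mm and the log model 0.22–0.80 mm. In one law the plain line is slightly better than the log (0.29 against 0.31 mm).
8. Across all these declining settings k was positive, and the correlation of prediction with true thickness ran from −0.39 to −0.94.
9. With 30% noise and exponential decay, y = kx gives 1.74–2.92 mm (2–5 mm) and 1.45–2.26 mm (1–4 mm). The free line gives 0.47–0.76 mm and the log model 0.28–0.75 mm.

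**The case against.** - **The harm is conditional.** The documents give no pilot or attenuation data, and they hypothesise the opposite direction. This stands: the reversed ranking rests on a premise from outside the plan. The positive slope and the zero intercept do not. The remedy does not need the premise either, because a free line contains y = kx as the case of zero intercept and positive slope. If the sponsor's direction is right, the data will show it.
- **x is not defined.** If x meant attenuation, −ln(I/I₀) with I₀ known, a line through the origin would suit exponential decay, with RMSE 0.15–0.73 mm over the same μ values (2–5 mm, 15% noise). The background paragraph, however, defines the quantity as light seen outside the stomach, and the algorithm is to work from imaged transmittance. Attenuation is a possible repair, not what is written.
- **The plan also speaks of correlating light with thickness, and a negative coefficient would expose the wrong direction.** This softens the point. But no coefficient is named, and no rule says that a negative one would replace y = kx.
- **The statistical methodology section may exist elsewhere.** That cannot be settled from the supplied text. If it exists, it has to agree with the formula in Methods.
- **The raw pairs are kept, so another model could be fitted later.** True, but a model chosen after seeing the stated one fail is no longer the planned analysis.
- **The recommended model may gain little.** This stands in weak-signal settings. With light falling only to 80% and 30% noise, the free line and the log model both give 0.85 mm against 0.87 mm for the mean. The stated formula is still clearly worse there, at about 1.5 mm.

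**Conclusion.** The concern holds: the formula is wrong as written and should be corrected before the algorithm is built. It is certain that y = kx forces predicted thickness to rise with light and to be 0 mm at no light. On the single premise that a thicker wall passes less light, it also reverses the order of sites and does worse than a constant prediction under any shape of decline. Under exponential decay its RMSE is about 1.5 to 3.3 times that of the mean (1.32/0.87 to 2.87/0.87). The millimetre figures depend on assumed decay laws, noise and thickness ranges, and are in-sample; the sign of the error does not depend on them.

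**What to change.** Replace the y = kx sentence in Methods with wording such as: *Thickness will be modelled on light intensity with an estimated intercept and an estimated slope, expected to be negative, for example thickness = b0 + b1·ln(intensity); the functional form (linear or log) will be checked against the data.* State which variable is the predictor and which the outcome.

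In the background paragraph, replace direct proportionality with the hypothesis that transmitted light decreases as the wall thickens, and say that the direction will be tested.

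Report RMSE or centred R-squared against a mean-only prediction, so that a model worse than none is visible. If a statistical methodology section exists, reconcile it with this model.

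The cost is two sentences of wording, one extra coefficient, a linear-versus-log check and a mean-only benchmark. No new patients or measurements are needed.
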